5.4 STORAGE CONDITIONS AND STABILITY

Investigational product will be stored at room temperature (20°C to 25°C or 68°F to 77°F) and in dry place, protected from light. If the IP temperature extends outside the 20-25°C range, a temperature excursion must be documented in IP specific temperature log. If the excursion is within 15-30°C, quarantine is not required, and the IP is acceptable for use. If the excursion is outside of the 15-30°C range, the IP must be quarantined until a decision on the stability of the IP is made by the Sponsor. If the excursion goes beyond the range of 15-30° C it will be considered as a protocol deviation. Storage condition will be maintained during shipment. All IP supplies in the study will be stored in a secure location with access limited to the Site Pharmacist or the Investigator designated site staff.

Refer to the pharmacy manual/site investigational product manual for additional guidance on study drug preparation, handling and storage.

5.5 BLINDING

The study will be performed in a double-blind manner. All study drug will be supplied in identical packages and study drug kits. The study drug tablets will be similar in color, smell, taste and appearance, thereby maintaining double-blind conditions.

The study blind should not be broken except in a medical emergency where knowledge of the study drug received would affect the treatment of the emergency.

The blind must only be broken following a discussion on a case-by-case basis, at the discretion of the Sponsor/Medical Expert. If an emergency unblinding becomes necessary, the PI should notify the Sponsor/Medical Expert, if possible, before unblinding. If it is determined that unblinding is necessary, a scratchcard will be decoded to reveal the treatment received by the patient. All cases resulting in an unblinding event will be documented and reported to the

Approved by: [name]	Protocol No. SARO.17.009 Version No.: 5.0
------------------------------------	--

 Zydus Discovery DMCC	CLINICAL TRIAL PROTOCOL Saroglitazar Magnesium – Phase 2A SARO.17.009	Confidential Page 49 of 82
--	---	-------------------------------

Medical Expert and the Sponsor. If the blind is broken, the date, time and reason must be recorded in the patient's eCRF/source document and any associated AE report completed.

The overall randomization code will be broken only for reporting purposes. This will occur once all final clinical data have been entered into the database, all data queries have been resolved, and the assignment of patients to the analysis sets has been completed.

5.6 METHOD OF ASSIGNING PATIENTS TO THE TREATMENT GROUPS

Patients will be randomly assigned in a 1:1 ratio to Saroglitazar Magnesium 4 mg Tablets and placebo. The block randomization schedule will be generated using SAS® software (Version: 9.4 or higher; SAS Institute Inc., USA).

5.7 SELECTION OF DOSES

Saroglitazar Magnesium is known to safely and effectively improve dyslipidemia by reducing TG, LDL cholesterol, very low-density lipoprotein (VLDL) cholesterol, non-high-density lipoprotein (non-HDL) cholesterol and increasing HDL cholesterol. In addition, Saroglitazar Magnesium can improve glycemic indices in diabetic patients by reducing fasting serum glucose and glycated hemoglobin. Considering the association between insulin resistance, dyslipidemia and the development of NASH, Saroglitazar Magnesium could potentially benefit patients with NAFLD including those with NASH and PCOS.

Saroglitazar Magnesium 4 mg Tablets have favorably modified the lipid profile in dyslipidemic and hypertriglyceridemic patients during previously conducted Phase 2 and 3 studies.^{10, 13} Based on these results, Saroglitazar Magnesium 4 mg dose has been selected for this study.

5.8 CONCOMITANT THERAPY

All medications received by the subject at any time prior to the Screening Visit and taken within 3 months before the Screening Visit, during the interval between the Screening Period and Randomization and those taken throughout the trial will be recorded on the appropriate section of the eCRF. The site may rely on subject reports for this information. All subjects must be questioned about concomitant medication at each visit. All concomitant medication, both prescribed and over-the-counter, must be recorded in the eCRF. This includes drugs used on a chronic and as needed basis. Medications that are indicated as prohibited in the Exclusion Criteria must not be used after the Screening Visit during the interval between the screening period and randomization or during the trial.

The following treatment/drugs will be allowed during the study.

- Treatment for common illness during the study may be allowed.

Approved by: [name]	Protocol No. SARO.17.009 Version No.: 5.0
------------------------------------	--

 Zydus Discovery DMCC	CLINICAL TRIAL PROTOCOL Saroglitazar Magnesium – Phase 2A SARO.17.009	Confidential Page 50 of 82
---	---	-------------------------------

- Stable antidiabetic and lipid lowering medications at least for the 3 months preceding screening.
- Stable doses of metformin or any treatment of PCOS at least for the 3 months preceding screening.
- For any required concomitant medication, the patient must be on a stable dose for 3 months at study entry and patients must continue with their current drug regimen without any change in dosage.

5.8.1 Subjects on Concomitant Anti-diabetic Medication

Subjects on anti-diabetic medication shall also be assessed at scheduled visits for hyperglycemia/hypoglycemia; rescue medication will also be permitted, if required. Patients on concomitant anti-diabetic medication will be provided with a glucometer and instructions for use. All point of care (POC) glucose measurements by the patient during the study period should be performed on the study provided glucometer. The investigational site will download/record the data from glucometer for assessment of glucose levels since the prior visit.

The patients should monitor their glucose levels as follows:

- Fasting blood glucose should be measured on at least two days in a week. These measurements should be done in the morning before having breakfast and when the subject has been fasting for a minimum of 10 hours.
- Spontaneous measurements of the blood glucose should be done in the event the patient suffers from suspected hypoglycemia. The investigator should inform the patients on recognizing the symptoms of hypoglycemia (i.e. palpitations, tremor, diaphoresis, hunger and/or cognitive impairment) and instruct them on the actions to be taken in accordance with standard-of-care.

The American Diabetes Association (ADA) recommends the following treatment for non-severe hypoglycemia during which a patient is safety willing and able to consume oral treatment.

1. Consume 15-20 grams of glucose or simple carbohydrates
2. Recheck your blood glucose after 15 minutes
3. If hypoglycemia continues, repeat #1 & #2
4. Once your blood glucose returns to a normal level, consume a small snack if your next planned snack or meal is greater than 1 hour in the future

Approved by: [name]	Protocol No. SARO.17.009 Version No.: 5.0
------------------------------------	--

 Zydus Discovery DMCC	CLINICAL TRIAL PROTOCOL Saroglitazar Magnesium – Phase 2A SARO.17.009	Confidential Page 51 of 82
---	---	-------------------------------

Examples provided by the ADA of items containing 15 grams of simple carbohydrates include:

- Glucose tablets (follow instructions on the package)
- Gel tube (follow instructions on the package)
- 2 tablespoons of raisins
- 4 ounces (1/2 cup) of juice or regular (non-diet) soda
- 1 tablespoon of sugar, honey or corn syrup
- 8 ounces of nonfat or 1% milk
- Hard candy, gumdrops or jellybeans (read package for amount to consume)

In the event of severe hypoglycemia when a patient is unconscious and possibly seizing, and/or unable to safely ingest carbohydrates, do not attempt oral treatment. If glucagon is available, this should be administered as soon as possible. If glucagon is not available, it is not able to be administered or persons witnessing the event do not feel able to handle the situation, emergency medical personnel should be summoned via calling 911.

Investigators shall advise subjects to report any/all hypoglycemic episodes occurring during the course of the trial as they will be recorded in the eCRF.

Treatment for such conditions should be initiated as soon as the need for treatment is identified by the investigator, in accordance with treatment guidelines and standard of care, and should be adjusted as necessary to treat the subject's condition(s). All treatment with these drugs must be recorded in the eCRF.

5.8.2 Previous and Concomitant Medications

Any medication the patient takes other than the study drug, including herbal and other nontraditional remedies, is considered a concomitant medication. All concomitant medications and any changes in the dosage or regimen of a concomitant medication for the 3 months preceding visit 1 until the end of the study (i.e., the safety telephone call) must be recorded in the eCRF.

5.8.3 Excluded Concomitant Medications

Patients are not permitted to take the following medications:

- Zileuton, parenteral nutrition and Vitamin E (>100 IU/day)
- Other drugs with potential effect on NAFLD such as Ursodeoxycholic acid, SAM-e, Betaine, Pentoxifylline, or Milk Thistle.
- Thiazolidinediones (pioglitazone, rosiglitazone), chemotherapy or other investigational medications during the study duration.

Approved by: [name]	Protocol No. SARO.17.009 Version No.: 5.0
------------------------------------	--

 Zydus Discovery DMCC	CLINICAL TRIAL PROTOCOL Saroglitazar Magnesium – Phase 2A SARO.17.009	Confidential Page 52 of 82
---	---	-------------------------------

- Patients are not permitted to take medications which causes hepatic steatosis (e.g., corticosteroids, amiodarone, methotrexate, tetracycline, tamoxifen, anabolic steroids, or valproic acid).
- The known CYP2C8 inhibitors/substrates are not permitted during the study (Appendix 1: List of Known CYP2C8 Inhibitors/Substrates).
- Patients are not permitted to take medications such as digoxin, warfarin, quinidine, prazosin, etc.
- Patients also should not take any non-allowed over-the-counter medications or complementary and/or alternative medications believed to have a potential impact that would affect the ability to evaluate the study data.

The doses of statins (simvastatin, pravastatin, atorvastatin, fluvastatin, lovastatin, rosuvastatin) or fibrates (clofibrate, fenofibrate) should remain stable throughout the study period as much as possible.

5.8.3.1 Permitted Concomitant Medications

With the exception of excluded concomitant medications, other medications that patients have been taking at stable dosages for at least 3 months preceding visit 1, i.e., lipid lowering drugs and drugs for glycemic control, will be permitted as concomitant medications, including antidiabetic drugs such as metformin, sulfonylureas, dipeptidyl peptidase 4 inhibitors and insulin. To the extent possible, patients should continue with their current regimen of medication without any change throughout the study. Allowed over-the-counter medications include acetaminophen (maximum 1 gram/day), ibuprofen (maximum 800 mg/day) or naproxen (maximum 440 mg/day) or antacids such as H2 receptor blockers or proton-pump inhibitors for shorter duration as per investigator discretion.

The PI should be alerted if, during the course of the study, a patient requires a new medicine or therapy or a change to an established dosing regimen. All medications that target NAFLD with PCOS or NASH, or have been suggested to target the underlying causes of NAFLD with PCOS or NASH, should be reviewed and agreed by the PI, Medical Monitor and Sponsor before being taken by the patient.

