 - d. Abnormal baseline platelet counts ($<150 \times 10^3$ uL).
 - e. Total serum bilirubin greater than the ULN (>1.3 mg/dL) (except in patient with known Gilbert Syndrome where TB up to 2.5 mg/dL is allowed)
 - f. Albumin <3.2 g/dL
 - g. Serum ALT or AST >250 IU/L
 - h. Lipase or amylase more than the ULN at baseline.
 - i. Serum creatinine ≥ 1.5 mg/dL
 - j. Renal impairment as demonstrated by baseline estimated glomerular filtration rate (eGFR) < 60 mL/min/1.73 m² (calculated using the CKD-EPI equation).
 - k. Total creatine kinase level more than the ULN at baseline.
5. Patient with INR >1.3
6. Patients who have used medications known to cause hepatic steatosis (e.g., corticosteroids, amiodarone, methotrexate, tetracycline, tamoxifen, anabolic steroids, or valproic acid) for more than 2 weeks in the past year.
7. Prior bariatric surgery.
8. Weight loss of more than 5% in the 3 months preceding screening.
9. Severe co-morbidities (e.g., advanced cardiac, renal, pulmonary, or psychiatric illness).

10. Known allergy, sensitivity or intolerance to Saroglitazar Magnesium, comparator or formulation ingredients (Saroglitazar Magnesium Micronized, Magnesium Oxide Light, Microcrystalline Cellulose, Anhydrous Lactose, Croscarmellose Sodium, Povidone k 30, Talc (luzena c), Colloidal Silicon Dioxide and Magnesium Stearate).
11. Use of antidiabetic and lipid lowering medications if the dose is not stable for at least the 3 months preceding screening.
12. Intake of Vitamin E (>100 IU/day) or multivitamins containing Vitamin E (>100 IU/day) 3 months before enrollment.
13. Use of drugs with potential effect on NAFLD/NASH such as S-adenosylmethionine (SAM-e), Betaine, Pentoxifylline, Thiazolidinediones (Pioglitazone, Rosiglitazone), Obeticholic Acid or Milk Thistle in the 3 months prior to screening.
14. Changing doses of statins (Simvastatin, Pravastatin, Atorvastatin, Fluvastatin, Lovastatin, Rosuvastatin) or Fibrates (Clofibrate, Fenofibrate) in the 3 months prior to enrollment.
15. Illicit substance abuse within the past 12 months.
16. Pregnant or breast-feeding females.
17. Poorly controlled diabetes with HbA1c >8.5%.
18. Use of total parenteral nutrition in the 6 months preceding enrollment.
19. Women with known Cushing syndrome or hyperprolactinemia.
20. Late onset congenital adrenal hyperplasia, androgen-producing tumors.

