9.7.2 Secondary Efficacy Analysis

9.7.2.1 Endpoints

The secondary efficacy endpoints are:

1. Change from baseline in Liver Enzymes/LFTs (ALT, AST, ALP, GGT, serum protein, albumin and total bilirubin) at Week 12 and Week 24.
2. Change from baseline in Insulin resistance (IR) measured by Homeostasis Model Assessment (HOMA) at Week 12 and Week 24.
3. Change from baseline in CK-18, hs-CRP, TNF α and liver stiffness measured by transient elastography/FibroScan at Week 24.

Document Title:	Statistical Analysis Plan		
Version Number:	Final 1.0	Date:	18Oct2024
Protocol Number:	SARO.17.009	Sponsor Name:	Zydus Therapeutics INC

4. Change from baseline in controlled attenuation parameter measured by transient elastography/ FibroScan at Week 24.
5. Change from baseline in body weight, body mass index (BMI) and waist circumference at Week 12 and Week 24.
6. Change from baseline in MRI-derived total liver fat index and total liver volume at Week 24.
7. Change from baseline in serum lipid profile and lipoproteins (TG, TC, HDL, LDL, sdLDL, VLDL, ApoA and ApoB) at Week 12 and Week 24.
8. Change from baseline in Sex hormone binding globulin (SHBG) level at Week 12 and Week 24.
9. Change from baseline in ovarian function (Total testosterone, 17-hydroxyprogesterone, free testosterone, luteinizing hormone, follicle-stimulating hormone, LH-to-FSH ratio and estradiol) at Week 12 and Week 24.
10. Change from baseline in free androgen index at Week 12 and Week 24.

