9.7.2.2 Analysis Strategy

The analysis for the secondary efficacy endpoints performed as below:

For the analysis of the secondary endpoints, i.e., Change from baseline in Liver Enzymes/LFTs, Insulin resistance (IR) measured by HOMA, CK-18, hs-CRP, TNF α , liver stiffness, controlled attenuation parameter, body weight, body mass index (BMI), waist circumference, total liver fat index, total liver volume, serum lipid profile and lipoproteins, sex hormone binding globulin level, ovarian function parameters and free androgen index. The analysis of covariance ANCOVA model will be applied separately at each visit as appropriate. The model will include treatment as a fixed effect and the corresponding baseline values of the endpoint as a covariate.

For each visits the estimate of the LS Means for treatment groups and its 95% confidence interval, LS Mean for treatment group difference (Saroglitzaz magnesium 4 mg – Placebo) and its 95% confidence interval of the LS Mean for treatment group difference, and p-value to check the significance difference at 5% level of significance will be generated from ANCOVA model. These analyses will provide the treatment effect at each visit while controlling for baseline differences

Descriptive summaries will be provided for all the secondary efficacy endpoints at each scheduled visit by treatment group. All secondary efficacy analysis will be conducted primarily based on the PP population and analysis, based on mITT population will be considered as supportive analyses .

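### HOMA is analysed with insulin-treated women included, although injected insulin can enter the index; the main HOMA ANCOVA should be limited to women not on insulin at randomisation (minor)

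*Protocol*

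**What the plan says.** **Who may be in the trial.** Diabetes is excluded only when control is poor: exclusion criterion 17 reads "Poorly controlled diabetes with HbA1c >8.5" (per cent). Protocol 5.8.3.1 lists the permitted glucose-lowering drugs as "antidiabetic drugs such as metformin, sulfonylureas, dipeptidyl peptidase 4 inhibitors and insulin", provided the dose was stable for at least 3 months before Visit 1.

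**What may change on study.** Protocol 5.8 requires women to stay on their regimen with the dose unaltered. Protocol 5.8.3.1 is softer: "To the extent possible, patients should continue with their current regimen of medication without any change throughout the study". For women on antidiabetic medication, Protocol 5.8.1 adds that "rescue medication will also be permitted, if required", and that treatment is to be started "in accordance with treatment guidelines and standard of care, and should be adjusted as necessary".

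**How HOMA is analysed.** Secondary endpoint 2 in SAP 9.7.2.1 is "Change from baseline in Insulin resistance (IR) measured by Homeostasis Model Assessment (HOMA) at Week 12 and Week 24". SAP 9.7.2.2 specifies an ANCOVA at each visit: "The model will include treatment as a fixed effect and the corresponding baseline values of the endpoint as a covariate". Each comparison gets a p-value at the 5% level, in PP first and mITT as support.

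**What is silent.** No section treats insulin users separately for HOMA. The PP rule on deviations (SAP 8.2) looks only at the primary outcome. The subgroups in SAP 9.9 are ALT and country, and HOMA is not among their endpoints. The rule on concomitant medication in SAP 9.7.1.2 belongs to the primary estimand. The readable laboratory lists (Protocol 3.3) give FPG, HbA1c and plasma insulin, with no C-peptide.

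**The concern.** HOMA infers insulin resistance from the insulin a woman needs to hold her fasting glucose, and so presumes that the measured insulin is her own. If she injects insulin and the assay detects it, the result also depends on product, dose and time since injection. Without C-peptide the two sources cannot be separated afterwards.

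Three things could follow:

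- Erratic values in a few women inflate the residual variance.
- Women whose index does not carry the drug effect dilute the estimated difference.
- If insulin doses move differently in the two arms, calculated HOMA can differ for that reason.

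Insulin resistance is a named secondary objective and part of the rationale in Protocol 2.2. SAP 8.5 also closes recruitment at 60 rather than 90, so a handful of women weigh more.

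**Working it through.** The documents give no effect, SD or power for HOMA, so there is no planned figure to reproduce. The sizes below rest on assumptions and are illustrations.

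**Inputs from the documents**
- Recruitment closed at 60, dropout assumed at 20% (SAP 8.5): 60 × 0.8 = 48 women, 24 per arm.
- Model: treatment plus baseline HOMA (SAP 9.7.2.2).

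**Assumptions not in the documents**
- HOMA is calculated from fasting glucose and fasting insulin, and the assay detects injected insulin at least in part. Neither the formula nor the assay is stated.
- Share on insulin, *f*: 5–15%, which is 3–9 of 60 women. Zero is also possible.
- Ratio *r* of the SD of HOMA change in users to that in other women: 3–5.
- Users are spread evenly over the arms.

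**1. Precision**

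SE factor with users kept = √((1 − f) + f·r²). SE factor with users left out = 1/√(1 − f). Both are relative to the same number of women with none on insulin.

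| f | kept, r = 3 | kept, r = 5 | left out |
|---|---|---|---|
| 5% | √1.40 = 1.18 | √2.20 = 1.48 | 1.03 |
| 10% | √1.80 = 1.34 | √3.40 = 1.84 | 1.05 |
| 15% | √2.20 = 1.48 | √4.60 = 2.14 | 1.08 |

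At 10% the information lost by keeping users is 1 − 1/1.80 = 44% to 1 − 1/3.40 = 71%.

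Break-even: leaving users out gives the smaller SE when r² > (2 − f)/(1 − f). That is r > √(1.95/0.95) = 1.43 at 5% and r > √(1.85/0.85) = 1.48 at 15%. Below that ratio, keeping them is slightly more precise.

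**2. Dilution**

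If the true difference is δ in other women and users carry none of it, the pooled analysis estimates (1 − f)·δ: 0.95δ, 0.90δ and 0.85δ at 5%, 10% and 15%.

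**3. Both together, by simulation**

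An ANCOVA with treatment and baseline was simulated 4,000 times at 24 per arm. Assumed: true difference −1.0, residual SD 1.5, an added SD of 6 in users (r = √(1.5² + 6²)/1.5 = 4.1), no signal in users, unchanged doses.

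| f | mean estimate | power |
|---|---|---|
| 0% | −0.99 | 61% |
| 5% | −0.95 | 42% |
| 10% | −0.92 | 31% |
| 20% | −0.79 | 17% |

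**4. Bias between arms**

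Bias = f × (mean dose-related HOMA shift in users on saroglitazar − the same on placebo). If doses are unchanged, or change alike, this is zero. If every user on saroglitazar shifted by −3 and no user on placebo shifted, it would be −0.15 at 5%, −0.30 at 10% and −0.45 at 15%. The simulation with no drug effect gave −0.15 and −0.30 for the first two. This is an extreme pattern, not an expected value.

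**The case against.** **Doses are meant to be fixed.** Protocol 5.8 forbids dosage changes, and exclusion criterion 11 bars antidiabetic doses not stable for 3 months before screening. Under stable dosing a constant distortion partly cancels in the change score and is partly absorbed by the baseline covariate. This stands: the harm is then mainly noise and dilution, and *r* could be smaller than assumed.

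**A reader might infer that HOMA is biased in favour of saroglitazar.** The documents do not support that. It needs insulin doses to fall more on saroglitazar than on placebo, and no passage says they will. The adjustment wording in Protocol 5.8.1 follows directly on text about hypoglycaemia and does not mention insulin titration. Protocol 2.3 also credits the drug with insulin sensitisation in preclinical models, so a reduced insulin need could itself be partly a real drug effect. What remains is that 5.8.1 and 5.8.3.1 leave dose changes possible.

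**A reader might infer that HOMA in these women simply measures the injected dose.** That is too strong. The assay is not described, and own and injected insulin may be mixed. Such values are nevertheless not a valid measure of insulin resistance.

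**The number of users may be nil.** In women of 18–45 with HbA1c up to 8.5% it may be zero or one. This stands and limits the weight of the point.

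**The primary estimand already disregards concomitant medication.** That rule covers MRI-PDFF only. Disregarding other treatment also does not make an index valid where its input is contaminated.

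**A sensitivity analysis would be enough.** It would be a reasonable lesser step. Restricting the main analysis is preferred because the defect is one of measurement, the variable is fixed before randomisation, and the expected loss is small.

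**Conclusion.** The gap is real and minor. Women on insulin are eligible, and nothing in the plan keeps their HOMA values out of a tested secondary endpoint or accounts for them. With unchanged doses the consequence is loss of precision and some dilution. Bias between arms is possible but conditional on dose changes that differ by arm.

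The text is clear; the size is not. If 5–15% of women use insulin with 3–5 times the usual SD of change, the SE is 1.18–2.14 times larger, against 1.03–1.08 times after leaving them out. With no users the effect is zero. The primary MRI-PDFF result and the study's success criterion are unaffected.

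**What to change.** In SAP 9.7.2.2, before unblinding:

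1. Restrict the main HOMA ANCOVA, in PP and mITT alike, to women not on insulin at randomisation. Identify them from the medication record, which Protocol 5.8.2 collects from 3 months before Visit 1 and SAP 9.5 codes to ATC level 3 and preferred name, with start and stop dates. Because this is a pre-randomisation variable, the restriction itself does not disturb the comparison of the arms.
2. Keep the analysis of all women as supportive.
3. Report by arm the number on insulin at randomisation, and the number who start insulin or change its dose afterwards.
4. In the main analysis, do not set HOMA to missing after insulin is started on study. That would select on a consequence of treatment, and SAP 8.4 does not impute secondary endpoints. If wanted, do it only as a labelled sensitivity analysis.

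Protocol 5.8, 5.8.1 and 5.8.3.1 also differ on whether glucose-lowering treatment may change on study. They should be reconciled so that the counts in item 3 can be read against one rule.

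The cost is a few sentences in the SAP and one data filter, with no new data. The downside is a few fewer women in the HOMA analysis, and a slight loss of precision if users turn out to be little more variable than the rest.
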